### 6.3.2 Ultrasound Imaging

The ultrasound examinations will be performed by a qualified sonographer. Procedures and equipment for this trial will be used in accordance with typical clinical procedures. All trial procedures will be conducted in accordance with Good Clinical Practice. A modified Logiq 9 scanner (GE Healthcare, Milwaukee, WI) with a broad bandwidth curvi-linear array will be used in to obtain RF data (for SHAPE measurements) within the hepatic and portal veins. Both the experimental machine and software will be labeled as an investigational device with a GE provided label prior to beginning any clinical experiments (21 CFR 812.5). Ultrasound imaging will be performed at a transmit frequency of 2.5 MHz and the subharmonic obtained at 1.25 MHz. Using this setup, acoustic pressure amplitudes will all be below 1.21 MPa peak negative pressure, 2.19 MPa peak positive pressure. The SHAPE algorithm will be activated and the acoustic power will be adjusted to produce the maximum change in subharmonic amplitudes (i.e., maximizing the sensitivity of SHAPE). Subharmonic data from the microbubbles (i.e., SHAPE) will be acquired in 5 s segments during the infusion of the Sonazoid suspension. All measurements will be repeated three times.

During the examination, the subharmonic pressure estimates will be displayed on the Logiq 9 scanner, these estimates will be noted and the data will be stored on a PC. Data will be compared to the

transcatheter portal pressure measurements, which comprise the free and wedged hepatic venous pressure (FHVP and WHVP, respectively) and the hepatic vein pressure gradient (HVPG; measured as the difference between the WHVP and FHVP), which are acquired as part of standard of care for all patients undergoing trans-jugular liver biopsy at TJU and HUP.

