**Trial Procedures:** Subjects eligible for trial enrollment will be identified by the co-investigators, [name] (at TJU) and [name] (at HUP) from their patient population of subjects scheduled for a trans-jugular liver biopsy. The research coordinators for this study will explain the study to the patients at the respective clinical sites. The patient will be given time to consider the risks and benefits of the study and ask questions about participation. The coordinator will review the consent form with the patient and then the patient will be given the form to review. The patient, coordinator, and a study investigator will all sign the consent form. The patient will be given a copy of the signed consent form for their records.

After consenting to participate in this study, a full demographic profile, known drug allergies or intolerances, and review of the subject's medical/surgical history will be recorded. Patients with known cardiac shunts will be excluded from the study. If the subject is a woman of childbearing potential, she will have a urine pregnancy test (the results of which will be made available to the subject prior to study initiation).

Whenever a subject undergoes a trans-jugular liver biopsy with transcatheter free and wedged hepatic venous pressure measurements as part of their standard clinical care and agrees to participate in the study, we will perform the corresponding SHAPE measurement within the 3 hours of post-recovery observation to ease transportation for patients and ensure that hydration status and other variables, which could potentially affect portal pressures, are equivalent. Administration of Sonazoid will be performed under

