## 3. TRIAL DESIGN

This is an open-label, non-randomized trial that will be conducted at two clinical sites, Thomas Jefferson

University (TJU) and the Hospital of the University of Pennsylvania (HUP). Enrolled patients undergoing trans-jugular liver biopsy will receive a continuous infusion of Sonazoid® (GE Healthcare, Oslo, Norway) co-infused with 0.9% NaCl solution over a 5-10 minute time period using the setup and infusion rates described in GE Healthcare (GEHC) Protocol Supplement provided in Appendix B. Ultrasound imaging will be performed using a Logiq 9 scanner with a 4C transducer (GE Healthcare, Milwaukee, WI) and the SHAPE algorithm will be used to measure pressure values in the hepatic and portal veins. Data will be stored on a PC and compared to pressure-catheter measurements, which are taken as part of the standard of care for all patients undergoing a trans-jugular biopsy. Subjects identified in the initial examination as having portal hypertension (by HVPG results) will be monitored by SHAPE for up to 18 months. These subjects typically have surveillance CT or MRI scans every 6 months to check for liver cancer and at those times a repeat SHAPE examination will be performed (ideally within 2 weeks). Any repeat transjugular biopsies performed in this population will also trigger a repeat SHAPE study. Results of blood test evaluations (performed every 3 months in this population), medication, concomitant imaging study or procedure (including endoscopies) done as standard of care will be noted. The end point for this part of the study will be any one new complication (e.g., liver cancer) or a marked worsening in any complication, liver transplantation, death, or the end of the clinical trial participation (up to 18 months). On an average, these patients will be monitored three times during the course of this clinical trial.

A full demographic profile, known drug allergies or intolerances, and review of the subject's medical/surgical history will be recorded. If the subject is a woman of childbearing potential, she will have a urine pregnancy test (the results of which will be made available to the subject prior to study initiation).

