### 3.1 Trial Duration

Individual participation in this trial will be limited to ultrasound imaging studies within the two hour period following a trans-jugular liver biopsy (during which their hepatic wedge pressure will be measured

with a pressure catheter as part of the standard of care at TJU and HUP). Patients are monitored for two hours (1 hour post Sonazoid injection). The entire ultrasound imaging protocol will require approximately one hour. Subjects identified in the initial examination as having portal hypertension (by HVPG results) will be monitored by SHAPE for up to 18 months. These subjects typically have surveillance CT or MRI scans every 6 months to check for liver cancer and at those times a repeat SHAPE examination will be performed. Any repeat trans-jugular biopsies performed in this population will also trigger a repeat SHAPE study. Moreover, these patients will have a complete blood test every 3 months and these clinical variables (platelets, albumin, MELD, etc.) as well as any medication will be recorded. Finally, most subjects with portal hypertension will undergo an endoscopy examination every 1 to 2 years [de Franchis 2005; Merkel et al. 2004]. Results of any concomitant imaging study or procedure (including endoscopies) will be noted. The end point for this part of the study will be any one new complication (e.g., liver cancer) or a marked worsening in any complication (e.g., MELD scores), liver transplantation, death, or the end of this clinical trial (after 3 years). On an average, these patients will be monitored three times during the course of this clinical trial. The time to reach the end point will be noted if a new complication or a marked worsening in any complication occurs.

Subject recruitment is expected to last 3 years (April, 2014 – January, 2017). This includes monitoring disease progression and/or treatment response. Analysis and publication of results are expected to take an additional 2 months (January– March, 2017). Volunteer Registry Database forms will be submitted to the National Institute of Health’s Office of Regulatory Compliance and Quality at the completion of the research study.

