#### 5.3 Blinding and Unblinding Methods

This is an open-label trial; therefore, no blinding or unblinding procedures for the trial drug are required.

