## 6.7 End-of-Treatment and End-of-Trial Evaluations

### 6.7.1 Discontinuation of Subjects

Subjects will be free to discontinue trial participation at any time. The investigator will also discontinue any subject from the trial if, in the investigator's opinion, it is not safe for the subject to continue. The date the subject is withdrawn from a treatment and/or from the trial and the reason for discontinuation will be recorded on the CRF. For portal hypertension patients that will be monitored by SHAPE for up to 18 months, the end point will be any one new complication (e.g., liver cancer) or a marked worsening in any complication (e.g., MELD scores) or the end of their clinical trial participation (up to 18 months). The time to reach the end point will be noted if a new complication or a marked worsening in any complication occurs. The time to reach the end point will be noted.

Trial participation will be considered completed if the subject has met all of the following trial

requirements:

- Has received at least one infusion of Sonazoid
- Has undergone the complete ultrasound imaging study as described in this protocol

If a subject's participation in the trial is interrupted for any reason (e.g., because of an AE or if the subject is lost to follow-up) and the subject has met the criteria described above for completing the trial, the subject's trial participation will be considered completed. If a subject's trial participation is interrupted for any reason by the subject's or investigator's choice and the subject has not met all of the criteria listed above, then the subject will be considered a discontinued subject.

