### 7.2 Statistical Analyses

#### 7.2.1 Hypotheses

$H_1$ : Can patients with HVPG of 10 mmHg or greater be identified using SHAPE? The fundamental hypothesis is that a sensitivity of 89% and a specificity of 81 % can be achieved by using SHAPE measurements to identify patients with HVPGs of 10 mmHg or greater.

H2: A correlation coefficient of 0.82 will be achieved between in vivo SHAPE and HVPG measurements.

H3: A correlation coefficients above 0.90 will be achieved between SHAPE and repeat HVPG results.

H4: SHAPE will significantly differentiate responders from non-responders using clinical outcomes as the reference standard.

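### For H4, nothing keeps the follow-up SHAPE readings from whoever judges marked worsening or manages the patient, so the judged part of the reference standard can be influenced by the test it evaluates

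*Combined protocol and SAP*

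**What the plan says.** Section 7.2.1 states H4 as: "SHAPE will significantly differentiate responders from non-responders using clinical outcomes as the reference standard". It serves the second primary objective (Section 2), which concerns monitoring of progression or treatment response.

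- **Visibility of SHAPE.** Section 6.3.2 says: "During the examination, the subharmonic pressure estimates will be displayed on the Logiq 9 scanner, these estimates will be noted and the data will be"; the sentence then covers storage. The Synopsis says the same. Patients with portal hypertension have repeat SHAPE exams at about the time of their six-monthly surveillance imaging (Synopsis, Sections 3 and 3.1), so readings accumulate while the outcome is still open.
- **The end point.** After any new complication, Section 3.1 lists "a marked worsening in any complication (e.g., MELD scores), liver transplantation, death", or the end of the trial. The Synopsis and Section 3 have the same components. Section 6.7.1 omits transplantation and death. None of these places gives a threshold for worsening, names an assessor or provides for adjudication. Section 7.2.1 does not define a responder.
- **Whose patients.** The co-investigators identify subjects "from their patient population of subjects scheduled for a trans-jugular liver biopsy" (Synopsis and Section 4).
- **Data.** Section 7.2.2 puts SHAPE, HVPG and clinical variables in one database. Section 7.1 makes the investigator responsible for managing it.
- **Blinding.** Section 5.3 reads: "This is an open-label trial; therefore, no blinding or unblinding procedures for the trial drug are required". It does not mention test results or outcome assessment.
- **Independent review.** The medical monitor in Section 6.6.2 reviews serious and unexpected adverse events, not the H4 end point.

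**The concern.** A study that judges a test against clinical outcome needs the outcome to be settled without knowledge of the test. Here the reading is on the screen and written down, the outcome contains a component that someone must judge, and no rule separates the two.

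Two routes are open:

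- **Classification.** Someone who knows that SHAPE is high may more readily call a doubtful change a marked worsening. This builds agreement between SHAPE and outcome.
- **Management.** Someone who knows the reading may look harder for complications, which also builds agreement. Or they may change treatment and avert the event, which weakens it.

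H4 could therefore appear supported, or unsupported, partly because of who knew the reading. The plan does not record who knew SHAPE and when, so a later analysis could not separate this effect from real discrimination.

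**Working it through.** **1. Is the route closed anywhere?** The places where one would expect it to be closed are these:

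| Place | What it covers | Keeps SHAPE from classifier or clinician? |
|---|---|---|
| 5.3 Blinding | Trial drug only | No |
| 6.3.2 Imaging | Display, noting, storage | No |
| 6.6.2 Medical monitor | Serious and unexpected adverse events | No |
| 6.7.1 End point | Components, time to end point | No |
| 7.1, 7.2.2 Database | Names and identifiers removed; SHAPE and clinical data together | No |

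The investigational label on scanner and software does not restrict use of the reading either.

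**2. Which hypotheses are exposed?** For H1 and H2 the reference is the baseline catheter HVPG, taken during the biopsy procedure. SHAPE follows in the observation period afterwards, so it cannot alter that value. H3 uses repeat catheter HVPG, which is an instrument reading. The exposure is to H4.

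**3. Does the plan give a figure for H4?** No. Section 7.2.3 sizes the trial on aim 1 (259 to 278 subjects) and on the SHAPE-HVPG correlation (264 to 343). It gives no number monitored, event rate or effect size for H4. The size below is therefore an illustration, and every input is assumed.

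**4. Illustration.** Let SHAPE be unrelated to true outcome. Let a share b of patients be borderline and called worsened exactly when SHAPE is above the median. Let the rest have events at rate 0.35.

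- Proportion called worsened: e = 0.35(1 − b) + b/2
- Share of events decided by SHAPE: w1 = (b/2)/e
- Share of non-events decided by SHAPE: w0 = (b/2)/(1 − e)
- AUC = 0.5 + 0.25(w1 + w0), because a SHAPE-decided member of a pair raises the chance of correct ordering by 0.25
- Null standard error of the AUC in the rank test: √[(n + 1)/(12·n1·n0)], with n1 = ne and n0 = n(1 − e)

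For b = 0.10: e = 0.315 + 0.05 = 0.365; w1 = 0.05/0.365 = 0.137; w0 = 0.05/0.635 = 0.079; AUC = 0.5 + 0.25 × 0.216 = 0.554.

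At n = 80: n1 = 29.2, n0 = 50.8, standard error 0.0675, shift 0.054/0.0675 = 0.80. The rejection probability is P(Z > 1.96 − 0.80) + P(Z < −1.96 − 0.80) ≈ 0.126.

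If SHAPE decides only half of that 10% group and the rest fall as other patients do, the effective b is 0.05: e = 0.3575, w1 = 0.070, w0 = 0.039, AUC = 0.527.

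| Borderline cases decided by SHAPE | AUC | n = 80 | n = 120 | n = 160 |
|---|---|---|---|---|
| None | 0.50 | 5% | 5% | 5% |
| Half of 10% | 0.53 | 6.9% | 7.8% | 8.8% |
| All of 10% | 0.55 | 12.6% | 16.6% | 20.5% |

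Simulation with 2,000 runs per scenario gave 11%, 17% and 21% for the last row, in line with the approximation.

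**5. Other event rates.** A second simulation let a share f of all classifications follow SHAPE, with 50 to 200 monitored patients and 20 to 40% events. At f = 5% the AUC was about 0.525 and rejection 6 to 10%. At f = 10% the AUC was about 0.55 and rejection 8 to 23%.

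**The case against.** The case on the other side has real force.

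- **The route is inferred.** The protocol does not say who classifies worsening, who manages patients during follow-up, or that follow-up readings are passed on. A sonographer does the scan, and Section 7.2.3 places the biopsies in Interventional Radiology. A reader might infer from the recruitment wording that the co-investigators treat these patients and judge their outcomes; the documents do not say so. This stands: the route is open, not shown to be used.
- **Much of the end point resists judgement.** Death leaves almost no room for it, and transplantation and new liver cancer leave less than marked worsening does. MELD, the one example of worsening, is a score. This stands, and it narrows the point to the undefined component. That component weighs more if Section 6.7.1, without death and transplantation, is the operative definition.
- **Surveillance runs to its own timetable.** Imaging about every 6 months, blood tests every 3 months and endoscopy every 1 to 2 years are standard care. The protocol gives clinicians no SHAPE value to act on. This limits the management route without closing it, because follow-up tests are clinically driven.
- **H3.** A reader might also infer that SHAPE will prompt repeat biopsies and so select the H3 pairs. The text runs the other way: a repeat biopsy triggers a SHAPE exam. That inference is unsupported.
- **The illustration is upper-end.** It lets SHAPE settle every borderline case. Halving that brings rejection close to nominal.

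**Conclusion.** The concern holds for H4 only. As written, the plan lets the index test inform a judged part of its own reference standard, and no section prevents it.

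The possible size is modest to moderate. On the assumptions of a useless SHAPE, 35% events, 80 to 160 monitored patients and a 10% borderline group, false positives at a nominal 5% run from about 7 to 9% (SHAPE settles half of that group) to 11 to 21% (SHAPE settles all of it). None of these inputs is in the documents, so the figures show what could happen and do not estimate the bias in this trial.

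It would be tempting to conclude that the trial cannot say whether SHAPE tracks disease. That goes too far. An AUC of 0.53 to 0.55 produced by this mechanism would not pass for strong discrimination, and H1 to H3 rest on catheter pressures. The point merits a change because the remedy is cheap and cannot be applied after the outcomes have been classified.

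**What to change.** 1. State in Sections 5.3 and 6.3.2 that follow-up SHAPE values are stored under the study code, kept out of the clinical record, and not disclosed to the clinicians managing the patient or to the end-point classifier until that patient's follow-up closes.
2. Name an existing study investigator without access to SHAPE data to classify the H4 end point.
3. Have the investigators fix an objective rule for marked worsening, and the matching definition of responder, before the first follow-up exam. The choice of rule is theirs.
4. Reconcile the end-point components in Section 6.7.1 with those in the Synopsis and Sections 3 and 3.1.

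The cost is protocol wording, access settings in the existing database and some time from existing staff, with no added visits, patients or procedures. There are two limits. An investigational reading would not be available to clinicians during follow-up, although they keep HVPG and all standard tests. And masking SHAPE does not mask the HVPG in the clinical record, so a classifier could still be swayed by the measurement that SHAPE is meant to track; the objective rule is the main protection against that.

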#### 6.4 Efficacy Assessments

The findings of SHAPE will be correlated to the invasive catheter based measurements of portal vein blood pressure (i.e., HVPG) using least squares, multiple linear regression analysis with robust standard errors. Comparisons of sensitivities, specificities and accuracies for diagnosing portal hypertension with SHAPE will be conducted with an unpaired Student's t-test (using HVPG measurements as the reference standard). Receiver operating characteristic (ROC) curves will be computed using a continuous scale with HVPG cutoff levels of 10 and 12 mmHg. The optimal operating point (OOP) will be determined as the point closest to '0,1' on the ROC curve (representing 100% sensitivity and 100% specificity). All clinical variables (e.g., concomitant imaging results, presence of cancer or ascites, blood tests, fibrosis and MELD scores etc.) will also be compared to the SHAPE values.

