with HVPG cutoff levels of 10 and 12 mmHg. The optimal operating point (OOP) will be determined as the point closest to '0,1' on the ROC curve (representing 100% sensitivity and 100% specificity). All clinical variables (e.g., concomitant imaging results, presence of cancer or ascites, blood tests, fibrosis and MELD scores etc.) will also be compared to the SHAPE values. When both types of variables are ordinal or continuous, correlations will be calculated. When one type of variable is nominal and one continuous non-parametric rank order tests such as Mann-Whitney U-tests or Kruskal-Wallis tests will be performed [Rosner 1990]. All of the statistical analyses proposed for the human clinical trial will be repeated split by racial and ethnic groups to determine if clinically important race/ethnicity differences exist in the ability of SHAPE to diagnose portal hypertension.

All analyses and computations will be performed using NCSS/PASS 2008 and Stata 12.0 (Stata Corporation, College Station, TX), while the study database will be designed and implemented in Filemaker Pro 10.0 (Filemaker Inc, Santa Clara, CA). This database will contain all patient information (except names and other identifiers), including results of biopsies, HVPG and SHAPE measurements as well as the clinical variables.

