### 7.2.2 Analysis of Results

The findings of SHAPE will be correlated to the invasive catheter based measurements of portal vein blood pressure (i.e., HVPG) using least squares, multiple linear regression analysis with robust standard errors. Receiver operating characteristic (ROC) curves will be computed using a continuous scale with HVPG cutoff levels of 10 and 12 mmHg. The optimal operating point (OOP) will be determined as the point closest to '0,1' on the ROC curve (representing 100% sensitivity and 100% specificity). All clinical variables (e.g., concomitant imaging results, presence of cancer or ascites, blood tests, fibrosis and MELD scores etc.) will also be compared to the SHAPE values. When both types of variables are ordinal or continuous, correlations will be calculated. When one type of variable is nominal and one continuous non-parametric rank order tests such as Mann-Whitney U-tests or Kruskal-Wallis tests will be performed [Rosner 1990]. All of the statistical analyses proposed for the human clinical trial will be repeated split by racial and ethnic groups to determine if clinically important race/ethnicity differences exist in the ability of SHAPE to diagnose portal hypertension.

All analyses and computations will be performed using NCSS/PASS 2008 and Stata 12.0 (Stata Corporation, College Station, TX), while the study database will be designed and implemented in Filemaker Pro 10.0 (Filemaker Inc, Santa Clara, CA). This database will contain all patient information (except names and other identifiers), including results of biopsies, HVPG and SHAPE measurements as well as the clinical variables.

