### 7.2.3 Sample Size Calculation

As the most clinically important aim, the sample size analysis is based on specific aim 1 where each patient represents an independent entity. Based on our pilot study, the sensitivity and specificity of

SHAPE for the diagnosis of portal hypertension (i.e., HVPG > 10 mmHg) is 89% and 88%, respectively [Eisenbrey et al. 2013]. However, the confidence intervals achieved in the pilot study were (due to the limited sample size) very wide (worst case scenario: 52–100%). Hence, a power analysis was performed using NCSS/PASS 2008 (NCSS, East Kaysville, UT) to estimate the number of cases required to produce clinically acceptable 95% two-sided confidence intervals (for one correlation) [Newcombe 1998]. Table 2 below illustrates sample size calculations for the number of independent observations needed in the study population based upon 95% two-sided confidence intervals ranging from 0.06 to 0.10 for one correlation. A sample size between 259 and 278 subjects will provide 95% confidence intervals from 0.84 to 0.92 (i.e., a width of 0.08). A similar analysis was conducted based on the correlation between SHAPE and HVPG of 0.82 obtained in our pilot study [Eisenbrey et al. 2012a]. In that case to demonstrate that SHAPE can accurately measure HVPG values with a correlation coefficient of 0.82 requires between 264 and 343 patients (for confidence interval widths of 0.08 and 0.07, respectively). Hence, we selected a sample size for this study of 300 subjects.

Table 2: Sample size calculations for different 95% confidence intervals in the human clinical trial.

Target width	Proportion (R)	Lower limit	Upper limit	Sample size (N)
0.06	0.88	0.848	0.908	483
0.06	0.89	0.857	0.917	450
0.07	0.88	0.842	0.912	359
0.07	0.89	0.851	0.921	335
0.08	0.88	0.836	0.916	278
0.08	0.89	0.845	0.925	259
0.09	0.88	0.830	0.920	222
0.09	0.89	0.839	0.929	207
0.10	0.88	0.824	0.923	181
0.10	0.89	0.833	0.933	170

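### The t-test planned for sensitivity, specificity and accuracy names no comparator and cannot assess H1; Section 7.2.2 chooses the operating point on the same data, with no interval and no allowance for that choice

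*Combined protocol and SAP*

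**What the plan says.** The Synopsis (Statistical Methodology) and Section 6.4 both say: "Comparisons of sensitivities, specificities and accuracies for diagnosing portal hypertension with SHAPE will be conducted with an unpaired Student's t-test". The only other term in the sentence is HVPG, named as the reference standard.

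H1 in Section 7.2.1 reads: "The fundamental hypothesis is that a sensitivity of 89% and a specificity of 81 % can be achieved by using SHAPE measurements", for patients with HVPG of 10 mmHg or more. Section 3 describes an open-label, non-randomized trial with no control arm.

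In Section 7.2.2 the t-test sentence is absent; the regression sentence runs straight into the ROC sentence: "multiple linear regression analysis with robust standard errors. Receiver operating characteristic (ROC) curves will be computed using a continuous scale". ROC curves are planned at 10 and 12 mmHg, and "The optimal operating point (OOP) will be determined as the point closest to '0,1' on the ROC curve". No interval for sensitivity or specificity is stated. The Synopsis and Section 7.2.2 add: "All of the statistical analyses proposed for the human clinical trial will be repeated split by racial and ethnic groups".

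Section 7.2.3 calls specific aim 1 the most clinically important and sizes it on interval width, "based upon 95% two-sided confidence intervals ranging from 0.06 to 0.10 for one correlation". The column of Table 2 that holds 0.88 and 0.89 is headed as a proportion.

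**The concern.** A reference standard defines sensitivity and specificity; it is not a second sample. The sentence therefore names a two-sample test without naming two samples. There are three candidate uses:

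- **H1.** This is a claim about the level of two proportions in one cohort. An unpaired two-sample test has nothing to compare.
- **Race and ethnicity groups.** These are different patients, so an unpaired test is reasonable.
- **The 10 and 12 mmHg cut-offs.** Both use the same patients, and those at 12 or above are a subset of those at 10 or above. The independence that the test assumes is absent.

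The documents do not say which use is meant. In Section 7.2.2 the only source of a sensitivity and specificity for H1 is an operating point picked to look best on the data that then supply the estimates. Nothing allows for that selection, and the interval on which the aim was sized does not appear. The headline accuracy figures would be read against 89% and 81% with an upward bias and no stated precision.

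**Working it through.** **1. The plan's own figure.** Inputs from Table 2: proportions 0.88 and 0.89, widths 0.06 to 0.10. The exact (Clopper-Pearson) 95% limits for x of n are lower = Beta(0.025; x, n−x+1) and upper = Beta(0.975; x+1, n−x), with x = p·n. At p = 0.88 and n = 278 they are 0.8359 and 0.9158 (width 0.0799); at p = 0.89 and n = 259, 0.8454 and 0.9254 (width 0.0800). All ten rows match in their limits, and each N is the smallest that meets its width. A Fisher-z interval for one correlation matches no row: width 0.08 would need 129 at 0.88 and 111 at 0.89. The same Fisher-z formula does reproduce the 264 and 343 quoted for a correlation of 0.82. Table 2 is therefore a one-sample binomial calculation, and the correlation label on it is wrong.

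**2. Unpaired test between independent groups.** Section 7.2.3 gives 30% African American and 66% Caucasian, so 90 and 198 of 300. With assumed HVPG-positive shares of 20% (18 versus 40 positives) and 50% (45 versus 99), 200,000 simulated t-tests on sensitivity give type I error of 0.054 and 0.047. For smaller groups, using the stated 4% and 10% shares, it is about 0.03 to 0.05, rising to 0.08 in the extreme case of 2 versus 40 positives. The test is adequate for the main contrast.

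**3. Unpaired test at 10 versus 12 mmHg.** Let n be the number at 10 mmHg or above, f the fraction of them at 12 or above, and assume one common SHAPE threshold with equal sensitivity p.
- True variance of the difference: p(1−p)/n × (1−f)/f.
- Variance the unpaired test assumes: p(1−p)/n × (1+f)/f.
- Ratio: (1−f)/(1+f). With f = 0.5 (assumed) this is 0.5/1.5 = 0.333.
- Type I error: 2 × [1 − Φ(1.96/√0.333)] = 0.0007 instead of 0.05. Simulation with n = 60, 150 and 210 gives 0.0005, 0.0008 and 0.0008.

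With a separate operating point per cut-off (bivariate normal, correlation 0.82, N = 300, several assumed shares), the true SD is 0.77 to 1.58 times the assumed one, so the error can go either way.

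**4. Operating point chosen on the same data.** Assumed model: HVPG-negative SHAPE values N(0, 1), HVPG-positive N(1.370, SD 0.401). This puts the population point closest to (0,1) at sensitivity 0.89 and specificity 0.81, the H1 values. In each of 20,000 simulated trials of 300 the closest point is selected, and the apparent value is compared with the true value at that threshold.

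| Assumed positive share | Positives / negatives | Sensitivity excess (points) | Specificity excess (points) |
|---|---|---|---|
| 20% | 60 / 240 | 3.0 | 0.5 |
| 50% | 150 / 150 | 1.4 | 1.0 |
| 70% | 210 / 90 | 0.9 | 1.6 |

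A bootstrap that repeats the selection (100 resamples, 1,000 runs) reduces the sensitivity bias from 2.98, 1.38 and 0.97 points to 0.92, 0.41 and 0.31, and the specificity bias from 0.30, 1.10 and 1.56 to −0.03, 0.40 and 0.47. The uncorrected figures differ slightly from the table because there are fewer runs.

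**5. The intervals that are not planned.** Exact 95% intervals at N = 300, with counts near the H1 values:

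| Assumed positive share | Sensitivity | Specificity |
|---|---|---|
| 20% | 53/60: 0.774–0.952 | 194/240: 0.753–0.856 |
| 50% | 134/150: 0.833–0.938 | 122/150: 0.742–0.872 |
| 70% | 187/210: 0.840–0.929 | 73/90: 0.715–0.886 |

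These show the precision a reader would need to see. They do not measure harm from the t-test.

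**The case against.** No section says that the t-test judges H1. The sentence speaks of comparisons in the plural, and the race and ethnicity split is a natural home for it, where step 2 finds it adequate. This stands. A reader might infer that the t-test distorts the error rate for H1; the documents do not support that.

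Section 7.2.3 gives neither a null value nor power, so this is a precision design, and a missing pass/fail rule is at most a missing detail. This also stands. A reader might go further and infer that the verdict on H1 is arbitrary. With 150 positives and true sensitivity 0.89, the chance of success is 0.98 if the interval need only not lie wholly below 89%, 0.51 if the estimate must reach 89%, and 0.01 if the lower limit must exceed it. Those three rules and the 50% share appear nowhere in the documents, so the figures are illustrative only.

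The optimism is modest: at a 50% share it is 1.4 and 1.0 points, against interval half-widths of about 5 and 6.5 points. That is fair, but on average it runs in one direction, and the plan neither shows nor corrects it.

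Finally, Table 2's header already speaks of a proportion, so that basis is partly stated. Only the exact binomial method is inferred, from the match in all ten rows.

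**Conclusion.** The point holds in limited form and should be fixed. The t-test sentence lacks a comparator. It suits independent groups, cannot assess the one-cohort levels in H1, and is invalid within the same patients; at 10 versus 12 mmHg its type I error is below 0.001 under a common threshold with f = 0.5, and unpredictable in direction with separate thresholds. Section 7.2.2, followed as written, gives sensitivity and specificity at a data-chosen point without an interval. The apparent values are too high by about 1 to 3 points for sensitivity and 0.5 to 1.6 for specificity.

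The omissions are plain on the text. The sizes depend on an assumed binormal model and on assumed HVPG-positive shares of 20% to 70%, because the documents give no share.

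**What to change.** 1. In the Synopsis and Section 6.4, limit the t-test sentence to a named contrast between independent groups, or use Fisher's exact test there. Delete the sentence if no such contrast was intended. For any same-patient contrast, such as 10 versus 12 mmHg, use a patient-level bootstrap that keeps each patient's results together.
2. In Section 7.2.2, report sensitivity among HVPG-positive patients, specificity among HVPG-negative patients and accuracy among all patients, each with an exact (Clopper-Pearson) 95% interval. Show them beside 89% and 81% as precision reporting, without a pass/fail claim.
3. Because those exact intervals treat the threshold as fixed, add a patient-level bootstrap that repeats the operating-point selection in every resample, and report optimism-corrected estimates beside the apparent ones.
4. In Section 7.2.3, correct the description of Table 2 from a correlation to a single proportion with exact binomial limits.

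The cost is protocol wording and a short bootstrap program, and the accuracy estimates will look slightly less favourable. Patients, procedures and data collection are unchanged.
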